Specific Aim 1: Determine the efficacy of RIPC to decrease frailty in the preoperative period. RIPC will decrease frailty as evidenced by increased 6MWT distance in pre-surgical colon cancer patients compared to standard of care colon cancer patients.

Specific Aim 2: Investigate whether RIPC improves functional recovery postoperatively. Frail colon cancer patients who undergo RIPC in the preoperative period will exhibit decreased frailty assessed by the 6MWT 4-weeks postoperatively compared to standard of care patients.

Inclusion Criteria:

- be between ages of 55-85
- have a diagnosis of non-metastatic colon cancer
- be scheduled for curative resection of non-metastatic colon cancer

Exclusion Criteria:

- condition which prevents walking
- any condition in which compression of the arm or transient ischemia is contraindicated (e.g. wounds in the arm)
- neurodegenerative disorder
- unstable angina in previous month
- MI during previous month

Procedures:

1. A member of the study team will pre-screen patients who fit the study criteria by looking at the clinical schedules of Drs. [name], [name] and [name] daily in Epic
2. When a potentially eligible patient is identified via Epic, the study team member will contact Drs. [name], [name] and [name] via email prior to the clinic visit. If the patient is identified as a surgical candidate by the surgeon, the surgeon will introduce the study team member to the patient at the conclusion of their surgical consult visit.
3. The study team member will explain the study to the patient in an unoccupied consult room in the colorectal surgery clinical area and obtain written informed consent if the patient is interested.
4. After obtaining consent, the next contact the study team will have with the patient will be in-person at the patient's preadmission testing (PAT) visit (standard of care for colon cancer patients), which will be approximately 3 weeks prior to planned surgery. At the conclusion of the patients PAT clinical visit, a study team member will measure 1) 10 meter walk test, 2) 6 minute walk test, 3) handgrip strength, 4) timed up and go test. These measures will all either be collected in the hallway of the PAT clinic area, or in the case of handgrip and timed up and go, in an unoccupied consult room. The time to conduct all tests is approximately 15-20 minutes.

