5. If the patient's 6-minute walk test distance is <80% of their age predicted distance [Predicted distance in 6 minutes (meters) = $868 - (\text{age} \times 2.9) - (\text{sex} \times 74.7)$ where age is in years and "1" is assigned for females and "0" is assigned for males.], they will continue in the study. If their 6-minute walk test distance is >80% of their age predicted norm, they will not be considered "frail" and will be excluded from the study.
6. After baseline measures of frailty are collected, the study participants will be randomized to receive either remote ischemic preconditioning (RIPC) or standard of care
7. Participants in the RIPC group will be given a handheld blood pressure cuff and instructions how to perform the RIPC procedure at home, daily, until their follow-up appointment prior to surgery
8. A member of the study team will call the study participants in the RIPC group 2-3 times to monitor compliance with the intervention.

9. Within 4 days of planned surgery, all participants will return to Froedtert Hospital and have their 6-minute walk test, 10 meter walk test, handgrip strength and timed up and go test re-evaluated at the 2nd floor Outpatient Rehabilitation Gym (Room 2112) by a member of the study team. This will be the conclusion of the intervention period for patients in the RIPC group.
10. Blood pressure variability data from the surgical procedure will be acquired from the anesthetic record
11. Participants will return to the 2nd floor Outpatient Rehabilitation Gym approximately 4 weeks after surgery to have the 10-meter walk test, 6-minute walk test, handgrip strength, and timed up and go test re-evaluated by a member of the study team. This will complete all study procedures.

Individual Procedures:

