All statistical analysis will be overseen by [name], Ph.D. (Co-I). Randomization of frail, pre-surgical colon cancer patients to the two intervention groups will be performed by [name] using randomized block designs (randomly chosen block sizes of 3, 6 and 9). [name] will work directly with a member of the study team. When a study participant is enrolled, he or she will receive a sequential number which will have a randomization schedule assigned to it (i.e. no intervention or RIPC), and this will be communicated to the study team.

Statistical analysis for the primary study outcome, the change in 6-minute walk test distance in the pre-surgical period, will be based on the analysis of covariance model

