(ANCOVA) with two predictors: group membership (RIPC vs. no intervention control) and the baseline value of 6MWT. To investigate power properties, we used a two-sample t-test (under the assumption that there will be no baseline effect of 6MWT). We plan to enroll 48 patients per group, but expect that 6 patients will be lost to follow-up based on an estimated attrition rate of 10-15% during the preoperative period. Thus, 42 patients will be available for comparing the intervention (RIPC) and control groups. Power calculations for a two sample t-test on 40 patients per group show that we will be able to detect a change in 6MWT distance of 30 meters from baseline to 48 hours pre-surgery between the groups with 82% power (SD=46 meters from literature review). A difference of ≥ 30 meters between the RIPC and standard of care groups is in agreement with previous work done by Gillis and colleagues which examined the effect of exercise prehabilitation on pre-surgical colon cancer patients and showed a difference in 6MWT distance of 41.6 meters between the exercise prehabilitation and standard of care groups. We will apply variance stabilizing transformations (natural logarithm or square root) to make ANCOVA residuals more normal if needed. If these transformations are not sufficient, we will proceed with a Mann-Whitney test. When we add 5% to 40 (asymptotic relative efficiency of Mann-Whitney to t-test is 96% under normality), then the Mann-Whitney test (a nonparametric alternative to the two-sample t-test) with 42 subjects per group will have similar statistical power when data comes from a normal distribution. We will use the same models for our pre-surgery secondary outcomes of self-selected walking speed during the 10-meter walk test, handgrip strength, and timed-up-and-go time.

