The analysis of changes in 6MWT from pre-surgical values to 4-weeks post-surgery will be conducted relying on variance stabilizing transformations and ANCOVA; however, the power calculations change. We expect to lose approximately 5 subjects per group from the test conducted 48-hours prior to surgery to 4-weeks post-surgery and have planned for 37 subjects per group at 4 weeks after surgery. At 35 subjects per group for t-test and 37 per group for Mann-Whitney test, the detectable difference in 6MWT distance at 82% power between the groups is 0.7 standard deviations. Based on others work in post-surgical colon cancer patients showing a SD of 46 meters, we expect to detect a difference between the groups of ≥ 32 meters. We will use the same models for our post-surgery secondary outcomes of self-selected walking speed during the 10-meter walk test, handgrip strength, and timed-up-and-go time.

We will explore the distribution of intraoperative blood pressure variability as measured by area above or below 135 mmHg or 95 mmHg, respectively and apply variance stabilizing transformations. There is no baseline value to adjust for in this analysis. At 40 subjects per groups for t-test and 42 per group for the Mann-Whitney test, the detectable difference at 76% power between the groups is 0.6 standard deviations, and at 0.7 standard deviations difference the power will be 87%. If the number of subjects with all blood pressure data between the upper and lower boundaries (meaning blood pressure variability = 0) is higher than 5, we will rely on exact Mann-Whitney test.

Risks:

1. Remote Ischemic Preconditioning (RIPC): there is a risk that the repeated occlusions of blood flow to arm during the RIPC protocol may cause tingling and numbness in the arm or hand during the cuff inflation period which may be uncomfortable for the study participants.
2. Clinical test of frailty: Study participants may feel tired during the 6MWT and there is a risk that patients could fall during either the 6MWT, 10 meter walk test, or timed up and go test (TUG).
3. Adverse event during 6MWT: there is a small chance that study participants could have a cardiovascular event during the 6MWT.
4. Loss of confidentiality

Safeguarding Against Risks:

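### The 4-week (Aim 2) analysis does not say which pre-surgical 6MWT is its reference or covariate; if it is the end-of-RIPC retest, part or all of any RIPC gain is removed

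*Combined protocol and SAP*

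**What the plan says.** - **Aim.** Specific Aim 2 opens with "Investigate whether RIPC improves functional recovery postoperatively". Its hypothesis is that RIPC patients "will exhibit decreased frailty assessed by the 6MWT 4-weeks postoperatively compared to standard of care patients".
- **Visits.** Under Procedures, the 6MWT is done at the PAT visit about 3 weeks before surgery, and randomisation follows (steps 4 to 6). It is repeated within 4 days of surgery (step 9), and of that retest the plan says "This will be the conclusion of the intervention period for patients in the RIPC group". It is done again about 4 weeks after surgery (step 11).
- **Primary model.** For Aim 1, Statistical Analysis specifies ANCOVA with "group membership (RIPC vs. no intervention control) and the baseline value of 6MWT". The contrast is the change "from baseline to 48 hours pre-surgery". If transformations fail, "If these transformations are not sufficient, we will proceed with a Mann-Whitney test".
- **4-week model.** The next paragraph states "The analysis of changes in 6MWT from pre-surgical values to 4-weeks post-surgery will be conducted" with transformations and ANCOVA. It defines neither the pre-surgical value nor the covariate. It gives 82% power for 0.7 SD (32 m, SD 46 m) with 35 per group, and applies the same models to post-surgery 10-meter walk, handgrip and timed up and go.

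**The concern.** The retest comes after randomisation and at the end of treatment, and it is itself the Aim 1 outcome. Subtracting it or adjusting for it takes out some or all of what RIPC achieved before surgery. A benefit gained before surgery and fully kept to 4 weeks could then look small or absent. A benefit that partly fades could look like an advantage for control, although 4-week function is equal or better under RIPC. The plan expects such a gain, because Aim 1 is powered for 30 m. The three post-surgery secondary outcomes inherit the same ambiguity.

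**Working it through.** **Which test is the reference?** The wording points both ways.
- *Towards the retest:* the plan uses the word baseline for the PAT test in the primary analysis ("from baseline to 48 hours pre-surgery") and in Safeguarding Against Risks. The 4-week paragraph uses a different term. The pre-surgery secondary outcomes are measured at the retest.
- *Towards PAT, or neutral:* patients are already called pre-surgical at randomisation ("Randomization of frail, pre-surgical colon cancer patients to the two intervention groups"), and the same adjective is applied to patients in the baseline eligibility text and to the whole period of the primary outcome. The 4-week paragraph counts losses from the 48-hour test, but a running count from 42 to 37 per group has to start there under either anchor.

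The reference is therefore undetermined.

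**Inputs.** From Statistical Analysis: 35 per group, SD 46 m, 0.7 SD at 4 weeks, 30 m for Aim 1. Assumed: two-sided alpha 0.05 (not stated in the plan), the slope b, and a covariate SD of 46 m.

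**The plan's own figure.** 0.7 × 46 = 32.2 m. SE = 46 × √(2/35) = 11.0 m, and 32.2/11.0 = 2.93. The noncentral t with 68 df gives 82.3%, so the stated 82% reproduces. The Aim 1 figure also reproduces: 40 per group and 30/46 give 82.1%.

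**What each model estimates.** Let D be the RIPC effect at 4 weeks, G the effect at the retest, and b the within-group slope of the 4-week value on the retest value.

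| Analysis | Estimates |
|---|---|
| 4-week value, or change from PAT, adjusted for PAT | D |
| Change from retest, adjusted for retest | D − b·G |
| Change from retest, unadjusted or adjusted for PAT; Mann-Whitney on that change | D − G |

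**Retest as covariate** (closest in form to the primary model), D = 32.2 m, G = 30 m. The 30 m covariate imbalance enters the standard error: SE = σ × √(2/35 + 30²/(68 × 46²)) = 0.252σ, with 67 df. The plan does not say whether 46 m is the SD of a distance or of a change. The low power takes σ = 46 m as the residual SD. The high power takes σ = 46√(1 − b²).

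| b (assumed) | Estimate | Power | Favours control when D is below |
|---|---|---|---|
| 0.5 | 32.2 − 15 = 17.2 m | 31-39% | 15 m |
| 0.7 | 32.2 − 21 = 11.2 m | 16-27% | 21 m |
| 0.9 | 32.2 − 27 = 5.2 m | 7-17% | 27 m |

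**Worst case, full subtraction**, D = 32.2 m, SD 46 m:

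| G | D − G | Power |
|---|---|---|
| 0 m | 32.2 m | 82% |
| 10 m | 22.2 m | 51% |
| 20 m | 12.2 m | 19% |
| 30 m | 2.2 m | 5% |

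The last row stays at 5-6% for SDs from 30 to 60 m. Here the contrast favours control when D is below G.

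**Simulation** (between-person SD 80 m assumed, SD of change 46 m, 35 per group, D = 32.2 m, G = 30 m). The 4-week distance adjusted for PAT gave 32 m with about 85% power. Change from retest adjusted for the retest gave about 6 m with 9%. Unadjusted change from retest gave about 2 m with 5%. With G = 0, all of these models recovered 32 m.

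**The case against.** The strongest reply is that Aim 2 opens by speaking of functional recovery, and change from just before surgery to 4 weeks is an ordinary measure of recovery. That stands in part. Change from the retest answers a legitimate question, and the aim is mixed. But the hypothesis that makes the aim testable compares groups at 4 weeks, and change from the retest does not test that when G is not zero.

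A second reply is that PAT may have been meant all along. The 4-week paragraph says that the power calculations change, which could imply that the rest of the primary approach carries over. Its power text also speaks of a difference in distance. This stands: a reader might infer that the plan has chosen the retest, and the documents do not support that.

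A third reply is that the 5% figure should not lead. This also stands. The plan names ANCOVA, and carrying over the primary model's form points to the retest as covariate, hence partial loss. Full subtraction needs an unadjusted change, a mix of anchors, or the Mann-Whitney fallback applied to change from the retest, none of which the plan states.

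**Conclusion.** The gap is real and worth closing: the 4-week analysis names no reference visit and no covariate, and one of the two candidate readings does not estimate the Aim 2 difference. The bias is conditional on the retest being meant and on RIPC producing a gain there. With a 30 m gain and a 32 m difference at 4 weeks, the retest-adjusted estimate falls to 5-17 m and power to 7-39% over assumed slopes of 0.9 to 0.5. The worst case is 2 m and about 5%. There is no distortion if PAT is meant or if the gain is zero.

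Two stronger inferences do not follow. The stated 82% is not wrong: it is correct for a 32 m contrast in whatever is analysed. The primary Aim 1 analysis is not affected, since its baseline is the pre-randomisation test. Confidence is medium, because the anchor, the slope, the size of the gain and the meaning of the 46 m SD all rest on assumptions.

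**What to change.** State that the Aim 2 outcome is 6MWT distance at 4 weeks, analysed by ANCOVA with group and the pre-randomisation PAT 6MWT as predictors. If the Mann-Whitney test is needed, apply it to change from PAT. Specify post-surgery 10-meter walk, handgrip and timed up and go in the same way, each with its own PAT value. Change from retest to 4 weeks may be kept as a separately labelled measure of decline or recovery across surgery, but not as the test of the 4-week hypothesis. If PAT was already intended, name that visit as the reference and name the covariate.

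The cost is wording only. All three sets of measurements are already scheduled, and the sample size does not change.

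### The 4-week 6MWT is analysed as change from a walk taken at the end of the RIPC period, so benefit gained before surgery is subtracted from Aim 2

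*Combined protocol and SAP*

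**What the plan says.** Specific Aim 2 (Hypothesis and Aims) is about functional recovery. Its operational sentence compares frailty, measured by the 6MWT 4 weeks after surgery, between patients who had RIPC and those who had standard of care.

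Procedures steps 4-6 place the baseline walk before randomisation. Step 9 places the pre-surgical walk within 4 days of planned surgery and calls it the end of the intervention period. Step 11 places the last walk about 4 weeks after surgery.

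Under Statistical Analysis, the primary outcome is the pre-surgical change in 6MWT, analysed by ANCOVA on group and baseline 6MWT. The 4-week analysis has its own paragraph. Its outcome is the change from the pre-surgical value to 4 weeks, analysed by ANCOVA; that paragraph does not name the covariate.

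The planned numbers run as follows:
- Enrolment: "We plan to enroll 48 patients per group, but expect that 6 patients will be lost to follow-up".
- Pre-surgical comparison: "Thus, 42 patients will be available for comparing the intervention (RIPC) and control groups" (48 - 6, so per group).
- After surgery: "We expect to lose approximately 5 subjects per group from the test conducted 48-hours prior to surgery to 4-weeks post-surgery", so the investigators "have planned for 37 subjects per group at 4 weeks after surgery".

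Power at 4 weeks is given as 82% for 0.7 SD with 35 per group, converted to 32 m with an SD of 46 m. The same models are to be used for the post-surgery walking speed, handgrip and timed-up-and-go outcomes. No analysis set or missing-data method is stated.

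**The concern.** A change score measured from a post-randomisation value does not estimate the effect of randomised treatment on the later outcome. If RIPC works before surgery, the RIPC arm starts the 4-week comparison from a higher value. A benefit that is fully kept then appears as almost no difference in change. That is the result Aim 2 hopes to see, and the planned analysis would usually report it as null. The better RIPC does on Aim 1, the more is taken away from Aim 2.

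The choice of anchor also makes the pre-surgical walk a condition for entering the 4-week analysis. A patient with a baseline walk and a 4-week walk, but no walk in the days before surgery, cannot contribute.

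**Working it through.** **1. The plan's own figures.** The documents state no alpha; two-sided 0.05 is assumed because it reproduces the stated power. Exact two-sample t-test power is 82.3% for 35 per group at 0.7 SD (stated 82%) and 82.1% for 40 per group at 30/46 SD (stated 82%). Also 0.7 x 46 = 32.2 m. The arithmetic is sound. The question is which contrast it applies to.

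**2. Inputs.** From the documents: pre-surgical effect Dpre = 30 m, 4-week effect D4 = 32 m, change SD 46 m, 37 per group at 4 weeks. Assumed: single-visit SD s of 70-100 m, equal at all visits, with the same correlation between every pair of visits. Because 46² = 2s²(1 - rho), rho = 1 - 2116/(2s²):
- s = 70: rho = 1 - 2116/9800 = 0.784
- s = 100: rho = 1 - 2116/20000 = 0.894

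**3. What the planned analysis estimates.** The expected contrast is D4 - b x Dpre. Here b = rho if the ANCOVA adjusts for the pre-surgical walk. It is 1 if the outcome is simple change, or if change is adjusted only for the randomisation baseline, which is balanced in expectation.

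Residual SD after adjustment is s x sqrt(1 - rho²), which gives 43.4 m (s = 70) and 44.8 m (s = 100). SE is residual SD x sqrt(2/37).

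| Analysis | Contrast | SE | Power |
|---|---|---|---|
| Adjusted for pre-surgical walk, s = 70 | 32 - 0.784 x 30 = 8.5 m | 10.10 m | about 13% |
| Adjusted for pre-surgical walk, s = 100 | 32 - 0.894 x 30 = 5.2 m | 10.41 m | about 8% |
| Change from pre-surgical walk | 32 - 30 = 2 m | 46 x sqrt(2/37) = 10.69 m | about 5% |

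**4. The same data adjusted for the randomisation baseline.** The contrast is the full 32 m. With 37 per group the SEs are again 10.10 and 10.41 m, and power is about 88% and 86%.

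**5. Does a repeated-measures model add more?** Take the planned losses as monotone: per group, 37 with all three walks, 5 with baseline and pre-surgery, 6 with baseline only. With a common baseline mean, the 4-week variance ratio is 1 - r² x (1 - 37/42), where r is the correlation of the pre-surgical and 4-week walks given baseline. With equal correlations r = rho/(1 + rho), which is 0.44 (s = 70) and 0.47 (s = 100). The 4-week SE goes from 10.10 to 9.98 m and from 10.41 to 10.27 m, a fall of 1.2-1.3%. Power becomes about 87-89%. For Aim 1 the variance ratio is exactly 1, because the 6 per group lost early have only a baseline walk.

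**6. Patients who miss the pre-surgical test but return.** The plan does not expect any. If 3 per group did, a baseline-adjusted ANCOVA would use 40 per group. Its SE would be 43.4 x sqrt(2/40) = 9.71 m (s = 70) or 10.01 m (s = 100); the repeated-measures model gives 9.61 or 9.89 m. Nearly all of that gain comes from the change of anchor.

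**The case against.** The strongest defence is that Aim 2 speaks of functional recovery, and recovery can mean the path from just before surgery to 4 weeks after. On that reading the 32 m is a further advantage on top of the pre-surgical one, and the stated 82% is correct for it. The 4-week paragraph also leaves its covariate unnamed.

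Part of this stands: change from the pre-surgical walk is a legitimate description of recovery. But the operational sentence of Aim 2 compares the arms at 4 weeks. Under the recovery reading the total 4-week advantage would have to be 30 + 32 = 62 m for simple change, or about 56-59 m with adjustment (32 + 0.784 x 30 to 32 + 0.894 x 30). The only comparable effect in the plan is the 41.6 m quoted for exercise prehabilitation. Naming the covariate does not rescue the analysis: with either walk as covariate the contrast is 8.5 m or less.

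A reader might go further and infer that both aims are restricted to completers, that this wastes precision or biases the result, and that attrition leaves the trial underpowered. The documents do not support this:
- A completer rule is never written. It is implied by the models and the planning counts.
- Aim 1 gains nothing from a repeated-measures model under the planned losses, and Aim 2 gains about 1% of SE.
- Enrolment already allows for the losses: power is computed at 40 and 35 per group, below the 42 and 37 expected.
- In simulations with poor walkers lost more often, completer bias was about 1 m or less.

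**Conclusion.** The 4-week analysis does not answer Aim 2 as its operational sentence puts it. If the benefit the trial is designed to find before surgery is sustained, the planned contrast shrinks from 32 m to about 5-8 m (adjusted for the pre-surgical walk) or 2 m (change without that adjustment). Power is about 5-13% at 37 per group, against the 82% stated.

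The size rests on the 30 m and 32 m effects and the 46 m SD from the plan, and on the assumed visit SD of 70-100 m with equal correlations. The direction does not depend on the assumed SD: whenever RIPC helps before surgery and the walks are positively correlated, part or all of that benefit is removed. If RIPC had no pre-surgical effect, nothing would be subtracted.

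The point is confined to the 4-week analysis. The post-surgery secondary outcomes share it as far as they use the same change-from-pre-surgery model. It is not a criticism of the primary Aim 1 analysis or of the sample size. The expected loss of 11 of 48 per group (23%) by 4 weeks, with no stated analysis set or missing-data assumption, is a gap in the plan worth closing in the same edit, but it does not drive this result.

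**What to change.** Define the Aim 2 estimate as the between-group difference in 6MWT at 4 weeks, adjusted for the randomisation baseline and including every randomised patient with a 4-week walk. Apply the same definition to the post-surgery walking speed, handgrip and timed-up-and-go outcomes. Keep change from the pre-surgical walk as a secondary description of recovery, and restate the 4-week power paragraph for the new contrast.

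Either of two models will do:
- An ANCOVA on group and baseline 6MWT, which mirrors the primary analysis.
- The 4-week contrast of a repeated-measures model with a common baseline mean. This also uses the pre-surgical walks of patients lost after surgery, under missing at random, for about 1% less SE. If it is chosen, the SAP should say how the planned transformations and the Mann-Whitney fallback apply.

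State the analysis set and the missing-data assumption in the same paragraph. Leave the Aim 1 analysis as planned. No new data or patients are needed. The cost is SAP wording, plus slightly more programming if the repeated-measures model is used.

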Since our goal is to examine the effects of RIPC on frail colon cancer patients, only participants who cover a distance $\leq 80\%$ of the age- and sex-predicted norms will be included in the study. Others have shown that pre-surgical colon cancer patients walk 65 – 74% of age- and sex-specific norms during the 6MWT.

3. 10 Meter Walk Test (10MWT): The 10 MWT is a validated measure to assess self-selected walking speed, considered by some the "6th vital sign". Slow walking speed has also been identified as one of five metrics which identify frailty, and is a strong predictor of adverse outcomes associated with frailty. In a hallway, participants will walk at their comfortable speed for 20 meters and be timed during meters 5-15 using a stopwatch to assess steady-state walking. 10MWT measures will be done in triplicate.

4. Handgrip Strength (HGS): Weak HGS has also been identified as a metric to identify frail patients. Patients with weak HGS are six times more likely to be frail, and HGS positively correlates with self-perceived fatigue, disability, morbidity, and mortality. Participants will squeeze a hydraulic hand dynamometer as hard as they can three times with their dominant hand and the maximal force generated will be recorded.

5. Timed up and Go (TUG): TUG is the time it takes a person to stand from an armed chair, walk three meters, turn around, walk back, and sit back down. Increased time during the TUG test has also been shown to be a sensitive and specific measure of frailty in elderly patients.

6. Intraoperative Blood Pressure Variability: We will query the Clinical Research Database Warehouse at the Medical College of Wisconsin and intraoperative blood pressure measurements will be extracted for each study participant. No other patient identifiers or clinical data will be revealed. BPV will be assessed as the product of magnitude x duration of SBP excursions outside the SBP range (>135 mmHg or <95 mmHg; area under the curve).

Statistical Analysis:

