1. RIPC: any discomfort related to the occlusion of blood flow to the arm during the RIPC should be minor and transient based on our experience performing the protocol. Based on our experience performing the procedure, and a multitude of other studies which have performed RIPC, we do not anticipate any issues with study participants performing the procedures at home.
2. Clinical tests of frailty: There is a very minimal risk of falling during the walking tests or the timed up and go test. The test administrators will provide contact guard assistance as needed and a gait belt can be worn by participants if deemed necessary by study staff. Participants may feel fatigued during the 6- minute walk test. All participants will be instructed to proceed at their own pace, and there will be chairs at both ends and in the middle of the hallway where the test is being conducted so participants can sit and rest if needed.
3. Adverse event during 6-minute walk test: Although risk of a sudden cardiac event in response to moderate intensity exercise (50-60% target heart rate) in elderly colon cancer patients is relatively rare, we have taken several measures to safeguard the health of our participants. First, all participants will be carefully screened by the PIs or their physician (Drs. [name], [name] or [name]) prior to exercise to determine the risk of an adverse response to exercise (e.g. uncontrolled hypertension or elevated resting vital signs). Blood pressure and resting heart rate will also be measured by [name] (clinical research assistant) immediately prior to beginning the 6MWT. Second, we will follow the guidelines for conducting the 6-minute walk test established by the American Thoracic Society. Specifically, we will ensure participants have not had unstable angina or a myocardial infarction in the previous month, that participants resting heart rate is below 120 beats per minute, systolic blood pressure is less than 180 mmHg, and diastolic blood pressure is less than 100 mmHg. The sites of 6MWT measurements [Peroperative Testing Clinic (baseline) and 2nd floor Outpatient Rehab Gym (48 hours pre-surgery and 4-weeks post-surgery)] are equipped with Automated External Defibrillators (AEDs), have physicians present at all times, and all members of the study team are certified in basic

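### A systolic pressure taken before randomization is available as a covariate for intraoperative blood pressure variability, but the plan does not use it and loses some precision.

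*Combined protocol and SAP*

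**What the plan says.** Individual Procedures, item 6, defines the outcome as the product of "magnitude x duration of SBP excursions outside the SBP range (>135 mmHg or <95 mmHg; area under the curve". The limits are the same for every patient.

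The last paragraph of Statistical Analysis says the score will be explored and transformed, and adds: "There is no baseline value to adjust for in this analysis". It gives power for a two-group comparison with 40 per group (t-test) or 42 (Mann-Whitney): "the detectable difference at 76% power between the groups is 0.6 standard deviations", with 87% at 0.7 SD. If more than 5 subjects score zero, the analysis moves to an exact Mann-Whitney test.

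Safeguarding Against Risks, item 3, states: "Blood pressure and resting heart rate will also be measured by" a clinical research assistant "immediately prior to beginning the 6MWT". The walk goes ahead only if "systolic blood pressure is less than 180 mmHg", among other conditions. The sites it lists cover the baseline, pre-surgical and post-surgical walks.

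Procedures, steps 4 to 6, put the baseline walk at the preadmission visit, use it to decide eligibility, and randomize afterwards.

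**The concern.** Every other outcome in the plan is adjusted for a baseline value. This one is not, and the stated reason is that none exists. Yet the safety procedures produce an SBP on each participant before allocation.

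That SBP is likely to be informative because the score uses absolute limits. A patient's usual pressure level can enter the score alongside true variability. Hypertension is not an exclusion criterion, and the numerical rule for the walk test admits SBP of 136 to 179 mmHg, already above the upper scoring limit.

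If SBP does predict the score, leaving it out keeps explainable variance in the error term. That matters somewhat here, because the plan puts power at only 76% for 0.6 SD.

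**Working it through.** **Is the reading pre-randomization?** Safeguarding item 3 ties it to the start of the walk and includes the baseline site. Procedures steps 5 and 6 place randomization after the baseline walk. So the baseline reading precedes allocation. Individual Procedures, item 2, also puts a 10-minute rest before that walk, so it should be a resting value.

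**Reproducing the plan's power.** Inputs from Statistical Analysis: n = 40 per group, d = 0.6 and 0.7 SD. Alpha is not stated for this analysis. Two-sided 0.05 is assumed because it reproduces the plan's figure; one-sided 0.05 gives 84.5% at 0.6 SD.

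- Noncentrality = d × √(n/2). For 0.6: 0.6 × √20 = 2.683. For 0.7: 0.7 × √20 = 3.130.
- Noncentral t with 78 df gives 75.5% and 87.1%. The plan states 76% and 87%, so it reproduces.
- Mann-Whitney at 42 per group, with n multiplied by 3/π: 75.7% and 87.2%. This also reproduces.

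**Adding SBP as a covariate.** If SBP correlates r with the transformed score, the residual SD is multiplied by √(1 − r²). The effect becomes d/√(1 − r²), with 77 df, and the equivalent sample size is 40/(1 − r²) per group. The documents give no r, so a range is assumed.

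| r (assumed) | Variance removed (r²) | 0.6/√(1 − r²) | Power, 0.6 SD | Power, 0.7 SD | Equivalent n per group |
|---|---|---|---|---|---|
| 0 | 0% | 0.600 | 75.5% | 87.1% | 40.0 |
| 0.1 | 1% | 0.603 | 75.9% | 87.4% | 40.4 |
| 0.2 | 4% | 0.612 | 77.2% | 88.4% | 41.7 |
| 0.3 | 9% | 0.629 | 79.3% | 90.0% | 44.0 |
| 0.4 | 16% | 0.655 | 82.4% | 92.1% | 47.6 |
| 0.5 | 25% | 0.693 | 86.4% | 94.6% | 53.3 |

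The gain at 0.6 SD runs from 0.4 points (75.9 − 75.5) to 10.9 points (86.4 − 75.5). At r = 0 the lost degree of freedom makes no visible difference.

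**Is the unadjusted test valid?** In 20,000 simulated null trials of 40 per group, with an assumed SBP SD of 18 mmHg and a correlation of about 0.65 with the score, the unadjusted t-test rejected in 5.1% and ANCOVA in 4.9%. The average group difference was about zero.

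**Chance imbalance.** The standard error of the between-group difference in mean SBP is SD × √(2/40). For an assumed SD of 15 to 20 mmHg this is 3.35 to 4.47 mmHg, so a difference above 5 mmHg in either direction has a probability of about 14% to 26%. The unadjusted test already allows for this through its error variance. Adjustment removes the part that SBP explains.

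**The case against.** The strongest reply is that the plan's sentence is correct. Elsewhere in the section the baseline covariate is the same measure as the outcome, and intraoperative variability has no such value. A reader might infer that the plan contradicts its own safety procedures. It does not: a clinic SBP is a different quantity. This is an overlooked covariate. What remains is that ANCOVA does not need the covariate to be the same measure as the outcome, and the plan gives no other reason for leaving the comparison unadjusted.

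A second reply is that the value of SBP here is unproven. Nothing in the documents links clinic SBP to intraoperative SBP. Area below 95 mmHg also counts, so the relation need not be monotone and a linear term could capture little. Participants are also screened for uncontrolled hypertension before exercise, so the number entering well above 135 mmHg is unknown. All of this stands, and it is why the gain is shown as a range that starts near zero.

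Third, the reading is described as a safety check, and the documents do not say it is kept as study data. That stands too, and the fix has to cover it.

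Fourth, with more than 5 zero scores the planned exact Mann-Whitney test takes no covariate, so adding ANCOVA alone could achieve nothing. This is right and changes the remedy.

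Finally, neither Specific Aim mentions this outcome, which limits the importance of the point.

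**Conclusion.** The point holds as a missed opportunity for precision. A pre-randomization SBP is measured, it plausibly predicts a score built on fixed limits, and the plan does not use it. At 40 per group and 0.6 SD, power is 75.5% unadjusted and about 76% to 86% adjusted for correlations of 0.1 to 0.5. At 0.2 or below the gain is under 2 points. These figures rest on an assumed two-sided alpha of 0.05, an assumed correlation, and a roughly linear relation after transformation.

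Two stronger readings are tempting and not supported. One is that an imbalance in usual pressure would pass for a treatment effect and so invalidate the comparison. Randomization balances SBP on average, and the unadjusted test keeps its type I error. The other is that hypertensive patients score high because the analysis is unadjusted. Any such scoring would come from the fixed limits, and adjustment changes no patient's score.

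**What to change.** - Record the SBP taken before the baseline walk as study data.
- Reword the Statistical Analysis sentence to say that the outcome has no baseline value of its own, and that pre-randomization SBP will be the covariate.
- Prespecify ANCOVA of the transformed score on group and that SBP, before any comparison by group. Do not use the SBP from the pre-surgical retest, because it is measured after treatment has begun.
- For more than 5 zero scores, or residuals that stay non-normal after transformation, name one method in place of the unadjusted Mann-Whitney test: a rank-based ANCOVA, or a van Elteren test (Mann-Whitney stratified by baseline SBP) with strata fixed in advance. The ANCOVA power figures above do not carry over directly to these tests.

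The cost is one form field, a few sentences and one degree of freedom. The measurement is already made. If the correlation proves weak, little is gained and almost nothing is lost.
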